### **G. Non-Serious AEs**

All non-serious adverse events should be reported to Janssen Scientific Affairs, LLC according to the timeframe outlined in the Research Funding Agreement section entitled Reporting of Data.

## H. Pregnancy

Initial reports of pregnancy must be reported to Janssen Scientific Affairs, LLC by the principal investigator **within 24 hours of becoming aware of the event** using the Serious Adverse Event Form. Abnormal pregnancy outcomes (e.g. spontaneous abortion, fetal death, stillbirth, congenital anomaly, ectopic pregnancy) are considered serious adverse events and must be reported using the Serious Adverse Event Form.

Any subject who becomes pregnant during the study must be promptly withdrawn from the study and discontinue further study treatment.

Because the effect of the J&J medicinal product on sperm is unknown, pregnancies in partners of male subjects exposed to a J&J medicinal product will be reported by the principal investigator within 24 hours of their knowledge of the event using the Serious Adverse Event Form. Depending on local legislation, this may require prior consent of the partner.

Follow-up information regarding the outcome of the pregnancy and any postnatal sequelae in the infant will be required.

## I. PQC Reporting

A PQC may have an impact on the safety and efficacy of the product. Timely, accurate, and complete reporting and analysis of PQC information from studies are crucial for the protection of patients, investigators, and Janssen Scientific Affairs, LLC, and are mandated by regulatory agencies worldwide. Janssen Scientific Affairs, LLC has established procedures in conformity with regulatory requirements worldwide to ensure appropriate reporting of PQC information. Lot and/or Batch #s shall be collected for any reports of failure of expected pharmacological action (i.e., lack of effect). The product should be quarantined immediately and if possible, take a picture.

All initial PQCs involving a J&J medicinal product under study must be reported to Janssen Scientific Affairs, LLC by the principal investigator **within 24 hours after being made aware of the event**. The J&J contact will provide additional information/form to be completed.

If the defect for a J&J medicinal product under study is combined with either a serious adverse event or non-serious adverse event, the principal investigator must report the PQC to Janssen Scientific Affairs, LLC according to the serious adverse event reporting timelines. A sample of the suspected product should be maintained for further investigation if requested by Janssen Scientific Affairs, LLC.

## **J. Reporting Procedures for Reporting Safety Data and Product Quality Complaints (PQCs) for Non-J&J Medicinal Products**

For SAEs, special reporting situations and PQCs following exposure to a non-J&J medicinal product under study, the principal investigator should notify the appropriate regulatory/competent authority or the manufacturer of that medicinal product (in the absence of appropriate local legislation) as soon as possible.

## **K. Individual Case Safety Report (ICSR)**

A valid ICSR must contain the four minimum criteria required to meet regulatory reporting requirements.

- an identifiable subject (but not disclosing personal information such as the subject's name, initials or address)
- an identifiable reporter (investigational site)
- a J&J medicinal product
- an adverse event, outcome, or certain special situations

The minimum information required is:

- suspected J&J medicinal product (doses, indication)
- date of therapy (start and end date, if available)
- batch or lot number, if available
- subject details (subject ID and country)
- Gender
- age at AE
- onset
- reporter ID
- adverse event detail (AE verbatim in English)
- onset date
- relatedness
- causality
- action taken
- outcome, (if available)
- J&J protocol ID

## **L. Transmission Methods**

The following methods are acceptable for transmission of safety information to Janssen Scientific Affairs, LLC:

- Electronically via Janssen SECURE Email service (preferred) to [contact]
- For business continuity purposes, if SECURE Email is non-functional: to [name]

- Facsimile (fax), receipt of which is evidenced in a successful fax transmission report
- Telephone (if fax is non-functional).

Please use the contact information and process information provided by Janssen Scientific Affairs, LLC.

## 7.6 Reporting to the FDA

The conduct of the study will comply with all FDA safety reporting requirements. **PLEASE NOTE THAT REPORTING REQUIREMENTS FOR THE FDA DIFFER FROM REPORTING REQUIREMENTS FOR HRPO/QASMC.** It is the responsibility of the Washington University principal investigator to report to the FDA as follows:

- Report any unexpected fatal or life-threatening suspected adverse reaction (refer to Appendix A for definitions) no later than **7 calendar days** after initial receipt of the information.
- Report a suspected adverse reaction that is both serious and unexpected (SUSAR, refer to Appendix A) no later than **15 calendar days** after it is determined that the information qualifies for reporting. Report an adverse event (refer to Appendix A) as a suspected adverse reaction only if there is evidence to suggest a causal relationship between the drug and the adverse event, such as:
  - A single occurrence of an event that is uncommon and known to be strongly associated with drug exposure
  - One or more occurrences of an event that is not commonly associated with drug exposure but is otherwise uncommon in the population exposed to the drug
  - An aggregate analysis of specific events observed in a clinical trial that indicates those events occur more frequently in the drug treatment group than in a concurrent or historical control group
- Report any findings from epidemiological studies, pooled analysis of multiple studies, or clinical studies that suggest a significant risk in humans exposed to the drug no later than **15 calendar days** after it is determined that the information qualifies for reporting.
- Report any findings from animal or in vitro testing that suggest significant risk in humans exposed to the drug no later than **15 calendar days** after it is determined that the information qualifies for reporting.
- Report any clinically important increase in the rate of a serious suspected adverse reaction of that listed in the protocol or IB within **15 calendar days** after it is determined that the information qualifies for reporting.

Submit each report as an IND safety report in a narrative format or on FDA Form 3500A or in an electronic format that FDA can process, review, and archive. Study teams must notify the Siteman Cancer Center Protocol Development team of each potentially reportable event within 1 business day after initial receipt of the information, and must bring the signed 1571 and FDA Form 3500A to the Siteman

Cancer Center Protocol Development team no later than 1 business day prior to the due date for reporting to the FDA.

Each notification to FDA must bear prominent identification of its contents (“IND Safety Report”) and must be transmitted to the review division in the Center for Drug Evaluation and Research (CDER) or in the Center for Biologics Evaluation and Research (CBER) that has responsibility for review of the IND. Relevant follow-up information to an IND safety report must be submitted as soon as the information is available and must be identified as such (“Follow-up IND Safety Report”).

### **7.7 Exceptions to Expedited Reporting**

Events that do not require expedited reporting as described in include:

- planned hospitalizations
- respite care
- events related to disease progression

Events that do not require expedited reporting must still be captured in the EDC.

## **8.0 PHARMACEUTICAL INFORMATION**

### **8.1 Study Drug Preparation**

OSHA Guidelines for handling cytotoxic drugs outlined in the American Journal of Hospital Pharmacy must be followed.

Decitabine (5-aza-2'-deoxycytidine) is supplied as a lyophilized powder for injection, 50 mg in 20-ml vials. When reconstituted with 10 ml of sterile water for injection, each ml will contain 5 mg of decitabine and 6.8 mg of  $\text{KH}_2\text{PO}_4$ . The reconstituted solution should be diluted to 0.1-1.0 mg/mL with pre-chilled 0.9% sodium chloride intravenous infusion, which has been cooled to 2-8°C. Reconstitution of the powder results in a rapidly decomposing solution. Unless used within 15 minutes of reconstitution, the diluted solution must be prepared using cold (2—8 degrees C) infusion fluids and stored at 2—8 degrees C (36—46 degrees F) for a maximum of 7 hours.

Decitabine will be administered per dosing schedule every  $28 \pm 4$  days.

The site according to institutional drug disposal procedures should discard any partially used vials.

Decitabine may be administered either as an inpatient or as an outpatient.

Recommended safety measures for handling and preparation includes masks, protective clothing, gloves (double glove with nitrile gloves) and vertical laminar airflow safety

cabinets.

#### **A. Supplier**

Decitabine is available commercially.

### **9.0 CORRELATIVE STUDIES**

#### **9.1 Correlative Studies Background**

##### **A. Methylation Changes**

Decitabine causes hypomethylation of DNA by inhibiting DNA methyltransferase (Section 1.3). DNA methylation is an important epigenetic event in modulating development, cellular differentiation, and proliferation. DNA methylation, primarily occurring at C5 of the cytosine ring within cytosine–guanine (CpG) dinucleotides, is frequently found clustered at gene regulatory sites such as promoter regions and results in transcriptional silencing of the affiliated gene. Depending on the promoter regions affected, DNA hypermethylation could lead to tumor suppressor gene silencing and ultimately tumorigenesis.

##### **B. Genome-wide decitabine induced DNA methylation signatures**

To determine whether decitabine treatment results in hypomethylation at consistent CpGs in AML blasts, we will perform whole genome bisulfite sequencing and assess for DNA methylation patterns in pre-treatment (Day 0), at Day 10 (C1D10), at Day 28 (C1D28), and in samples collected at relapse.

##### **C. Decitabine induced gene expression signatures**

To determine if changes in methylation induced by decitabine treatment correlate with gene expression changes, we will perform RNA sequencing on RNA extracted from bone marrow cells pre treatment (Day 0), on Day 10 (C1D10), and on Day 28 (C1D28) post decitabine.

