### 2.3 Exploratory Molecular Endpoints

1. To determine the proportion of patients who achieve mutation clearance to <0.1%, after 3 cycles of decitabine.
2. To determine whether PB or BM has the greater sensitivity for detecting residual mutation burden using a sensitive sequencing technology such as Haloplex.
3. To determine *TP53* clonal burden reduction after consolidation with stem cell transplantation using a sensitive sequencing technology such as Haloplex.
4. To determine whether decitabine induces consistent methylation signatures using whole genome bisulfite sequencing.
5. To determine whether decitabine induces consistent expression signatures using RNA sequencing, and whether these correlate with methylation signatures.

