#### **F. Secondary *Molecular Endpoints Analyses***

**Rate of patient specific mutation clearance** after 28, and 56 days of therapy will be determined using an Illumina based platform. We will compare the rate of mutation clearance between the patients who achieve a CR/CRi after 4 cycles and those who do not. We anticipate that we will identify between 6 and 25 exonic SNVs per case (the range obtained with >200 AML samples sequenced to date with whole genome or exome sequencing), and that the expected 95% confidence interval of the mean variant allele frequency will be  $\pm 2.56\%$  and  $\pm 1.25\%$ , respectively, if we assume an anticipated standard deviation of 3.2% within the same clone. The change of tumor burden over time and its association with clinical response will be assessed using 2-way ANOVA for repeated measurement data, followed by the ad-hoc multiple comparisons for between-group differences (e.g., responders vs. non-responders) at given time points as well as the between-time differences within each group. The resultant critical P values will also be corrected using permutation analysis for multiple testing.

The percent decrease in bone marrow methylcytosine will be calculated on day  $10 \pm 1$ . We will compare this reduction with previously published data and between the patients who achieve CR/CRi and those who do not. The correlation of peak plasma levels of decitabine with response will be assessed using 2-sample t-test or Mann-Whitney non-parametric rank-sum test as appropriate. The change of total bone marrow DNA methylcytosine from baseline and its association with both steady-state plasma drug levels and response will be assessed using 2-way ANOVA for repeated measurement data, followed by the ad-hoc multiple comparisons for between-group differences (e.g., responders vs. non-responders) and between-time

differences. Similar analyses will be performed for the correlation of expression profiles and SNP analysis with pharmacokinetic data.

The proportion of patients who achieve mutation clearance to <0.1%, after 3 cycles of decitabine, will be calculated and its 2-sided 90% confidence interval (CI) will also be provided. Using a sensitive sequencing technology such as Haloplex, the sensitivity of PB or BM for detecting residual mutation burden, as well as the *TP53* clonal burden reduction after consolidation with stem cell transplantation will be summarized using contingency tables.

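### Section 15.4.F correlates expression, SNPs, response and methylcytosine with pharmacokinetic data that no section collects, and no planned analysis relates expression to methylation, which is what objective 2.3.5 and section 9.1.C ask.

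*Combined protocol and SAP*

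**What the plan says.** **The question.** Objective 2.3.5 reads "To determine whether decitabine induces consistent expression signatures using RNA sequencing, and whether these correlate with methylation signatures". Section 9.1.C repeats it as the purpose of the RNA sequencing: "To determine if changes in methylation induced by decitabine treatment correlate with gene expression changes, we will perform RNA sequencing". Objective 2.3.4 and section 9.1.B ask a CpG-level question: "To determine whether decitabine treatment results in hypomethylation at consistent CpGs in AML blasts".

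**The assays.** Section 9.1.B plans whole genome bisulfite sequencing at Day 0, C1D10, C1D28 and relapse. Section 9.1.C plans RNA sequencing at Day 0, C1D10 and C1D28.

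**The analyses.** Section 15.4.F has one sentence on expression: "Similar analyses will be performed for the correlation of expression profiles and SNP analysis with pharmacokinetic data". On drug levels it says "The correlation of peak plasma levels of decitabine with response will be assessed using 2-sample t-test or Mann-Whitney non-parametric rank-sum test". Apart from a day 10 percent decrease in marrow methylcytosine, compared with published data and between responders and non-responders, its methylation analysis is of "The change of total bone marrow DNA methylcytosine from baseline and its association with both steady-state plasma drug levels and response".

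**The power.** Section 15.4.G claims 85% power for a 25 ng/ml difference in mean Cmax between 45 responders and 55 non-responders (SD 40 ng/ml, alpha 0.05). The same section enrols 60 patients.

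**The concern.** Two things do not fit together. First, 15.4.F relies on a variable, the plasma level of decitabine, that the trial does not appear to measure. Second, the relation that the objective names, expression with methylation, has no analysis, although both assays are planned at matching time points.

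At stake is the use of serial marrow samples and two genome-wide assays. The question is open by the protocol's own account: section 9.1.D notes that a methylation difference need not alter expression. With no stated method, the choice of genes, CpGs, time points and multiplicity control would be made after the data are seen, while the analyses that are written down could not be run.

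**Working it through.** **1. Is there a source for the pharmacokinetic data?** Each place where it could appear:

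- Section 2 (objectives): no pharmacokinetic objective at any level.
- Section 5.1 A to J (visit procedures): marrow, blood counts, chemistries, skin or buccal samples and banked blood; no drug-level draw.
- Section 9.2 (sample lists): marrow, peripheral blood, skin and buccal swab. Research blood goes into EDTA tubes and is processed to cryopreserved cells after red-cell lysis; no plasma aliquot is kept.
- Section 10 (calendar): no row label is for plasma or drug level. The table is imperfectly reproduced in the copy reviewed, but its row labels are readable and agree with 9.2.
- Section 11 (case report forms): no pharmacokinetic form.
- Section 1.3.A: pharmacokinetics appear as published background only. It gives a terminal half-life of 10 to 35 minutes. With a 1-hour infusion, a peak level needs a draw timed to the infusion, and none is scheduled.

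**2. Does the pharmacokinetic text fit this trial's size?** Inputs from 15.4.G: difference 25 ng/ml, SD 40 ng/ml, groups of 45 and 55, alpha 0.05 (taken as two-sided).

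- Standardised difference: 25/40 = 0.625.
- Noncentrality: 0.625 x sqrt(45 x 55/100) = 0.625 x 4.975 = 3.11.
- Two-sample t-test power: 86.8% (normal approximation 87.5%; with the Mann-Whitney efficiency factor 3/pi, 85.2%). The stated 85% is reproduced.
- Patients required: 45 + 55 = 100, against 60 enrolled.
- If 60 patients split in the same ratio (27 and 33, an assumption): noncentrality 0.625 x sqrt(27 x 33/60) = 0.625 x 3.854 = 2.41, and t-test power is 65.9%.

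The methylcytosine power statement in the same section uses the same group sizes. There the standardised difference is 20/15 = 1.33, and 27 against 33 still gives 99.9%, so the mismatch costs it little.

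**3. Does any analysis answer the molecular questions?**

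| Question | Variables needed | Analysis in 15.4 |
|---|---|---|
| 2.3.5, 9.1.C: expression with methylation | change in expression, change in methylation | None. Expression is paired only with pharmacokinetic data |
| 2.3.5: consistent expression signatures | expression by gene across patients | None |
| 2.3.4, 9.1.B: consistent CpGs | methylation by CpG across patients | None. Only percent or total marrow methylcytosine |

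Total methylcytosine is one number per sample. It cannot show which CpGs changed, or whether the same ones changed in different patients.

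**4. Could the missing analysis be done with planned data?** Yes. Both assays share Day 0, C1D10 and C1D28, and section 5.1 calls for morphologic assessment of the marrow at each of these, so blast percentage is available. C1D10 marrow is taken only in patients enrolled at the coordinating center, so Day 10 pairs will be fewer than total enrolment; the documents do not say how many.

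**The case against.** The strongest reply is that this is ordinary under-specification. Section 2.3 labels the items exploratory, and no sample size, interim rule, clinical endpoint or treatment decision depends on them. Sections 9.1.B and 9.1.C state the question, the assays and the time points, and exploratory sequencing is often left at that level of detail. This stands as far as severity goes. It does not dispose of the point, because 15.4.F is not merely silent: it states analyses that have no data.

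Two stronger readings are tempting, and the documents support neither.

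- A reader might infer that the trial cannot answer 2.3.5, or will test it against the wrong variable. Section 15.4.F never says that its expression sentence serves 2.3.5, and nothing bars the right analysis from the planned assays. The absence of a pharmacokinetic objective and the count of 100 patients suggest text that was not written for this design, rather than a deliberate choice of the wrong partner.
- A reader might infer that a chance signature will be reported as consistent, and try to say how many CpGs would qualify by chance. The plan does not define consistent, so any such count would rest on a rule, a CpG number and a rate of loss supplied by the reader. What can be said is that decitabine is described as a hypomethylating agent, so some overlap between patients is expected without any targeting, and the plan has no reference against which to judge it.

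**Conclusion.** The point holds as a mismatch within the plan. Section 15.4.F lists correlations of expression, SNPs, response and total methylcytosine with plasma drug levels that no section schedules. The matching power statement assumes 100 evaluable patients in a trial of 60. No analysis in 15.4 relates expression to methylation or works at CpG level.

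The size is qualitative for the missing analyses: none is stated for 2.3.4 or for either part of 2.3.5. For the Cmax comparison, power falls from about 87% to about 66%, assuming the 45:55 ratio carries over to 60 patients and that levels were measured at all.

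The finding rests on the protocol text alone; a separate laboratory manual could hold a sampling plan, but the protocol refers to none. The primary analysis of 1-year survival is unaffected, and the severity is low.

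**What to change.** 1. In 15.4.F, replace the correlation of expression profiles with pharmacokinetic data by a within-patient analysis. For each gene, relate the change in expression (C1D10 and C1D28, each minus Day 0) to the change in methylation at its regulatory CpGs, with false-discovery-rate control.
2. Include marrow blast percentage as a covariate. Treatment changes the cell mix, so expression and methylation could move together for that reason alone. State also whether both assays use the same cell fraction: 9.1.B speaks of blasts, 9.1.C of marrow cells.
3. Delete the remaining pharmacokinetic correlations in 15.4.F (SNPs, peak level with response, methylcytosine with steady-state level) and the Cmax power statement in 15.4.G, or state where the data come from and restate the power for the patients available.
4. If consistent CpGs are to be reported, define the term and judge it against a null that keeps each patient's overall loss and is matched on baseline methylation. A site that is unmethylated at Day 0 cannot lose methylation, and one that is highly methylated in every patient has more room to fall.

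The cost is SAP wording and some added analysis work. No new sample or visit is needed if the pharmacokinetic text is deleted and both assays use the same cell fraction; keeping the pharmacokinetic analyses would need a sampling plan unless another source is named.

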##### **D. DNA Changes**

Conventional chemotherapies in AML cause early termination of DNA synthesis (cytarabine) or topoisomerase inhibition (daunorubicin) that ultimately converge onto TP53 that, together with CDKN2A sense irreparable DNA damage and ultimately trigger cell cycle arrest and cell death. Therefore, it is not surprising that AML with defective TP53 are resistant to conventional chemotherapeutic agents. The effectiveness of decitabine that we observed in the cohort of patient with *TP53* mutation suggests that decitabine acts through a different, TP53 independent, mechanism. Interestingly, *Tp53* null mice develop normally, thus

suggesting that cell cycle exit via differentiation is intact in these mice. As mentioned in Section 1, treatment with decitabine does not lead to clone eradication. Morphologic blast clearance precedes mutation clearance, with the malignant clone often remaining detectable at low levels over time (Figure 4).

This is consistent with a model in which the proliferating cells of the malignant clone enter terminal differentiation after exposure to the drug, with the remaining quiescent stem cells carrying the mutation remaining dormant and eventually contributing to relapse when challenged to cycle.

[figure not shown]

Figure 4: Kinetics of blast clearance versus clonal burden: bone marrow blast reduction detected by morphology at C1D28 does not correlate with founding clone reduction at the same time-point.

Furthermore, difference in DNA methylation may not result in changes in gene expression. For example, AMLs with mutations in *DNMT3A* that result in significant hypomethylation in specific DNA regions, do not display differences in whole transcriptome compared to AML bearing wild type *DNMT3A*. This could be partially explained by the fact that DNA modifications (i.e. methylation status of gene promoters) are not the only determinant of gene transcription. Histones modifications, such as histones methylation, can alter chromatin structure through changes in the chemical moieties on the nucleosome surface and subsequently affect recruitment of the transcription factor machinery to specific DNA regions, silencing or activating gene transcription independently from promoter methylation.

